## 8.2 Visit Windows

In-clinic dialysis should start within 2 weeks after enrollment.

In-clinic dialysis sessions will be provided on Monday, Wednesday, and Friday (unless otherwise approved by Sponsor). In home dialysis sessions will be provided on Monday, Wednesday, Friday, and Saturday (unless otherwise approved by Sponsor).

Blood sampling will be performed on Wednesday (unless otherwise approved by Sponsor).

In-clinic dialysis will continue for a minimum of 4 weeks, and can be extended week by week to a maximum of 8 weeks until training competency is demonstrated. Timings for scheduled in facility visits will be calculated based on the date baseline completed. Treatment should occur at least three times per week as per standard protocol within the facility. The start of the transition phase will begin only after competency sign-off and will be 4 times during 1 week. The 8 week in home dialysis phase will begin after the transition phase and will be 4 times weekly for 8 weeks. To be included in the data analysis, scheduled visits occurring after competency sign-off must occur within  $\pm 3$  days of the expected time point.

## 8.3 Study Activities

Details of selected specific study activities are provided below.

Assessment	Details
physical exam	Heart, lungs, dialysis vascular access, and other body systems as appropriate
biochemistry	Sodium (Na), urea (BUN), potassium (K), creatinine (Cr), bicarbonate (HCO3), magnesium (Mg), phosphate (Phos), chloride (Cl), calcium (Ca), albumin (Alb), iron (Fe), transferrin saturation (TS), total protein (TP), ferritin (Fn), alkaline phosphatase (ALP), parathyroid hormone (PTH), total iron binding capacity (TIBC), aspartate transaminase (AST), alanine aminotransferase (ALT). BUN will be collected immediately before and after Quanta SC+ treatment.
hematology	Hemoglobin (Hb), hematocrit (Hct), white cell count (WBC), platelet count (PC), reticulocyte count (RC)

concomitant medication check	Change in concurrent medications, limited to the following: erythropoiesis-stimulating agents (ESAs), intravenous iron, phosphate binders, calcimimetics, and anti-hypertensive medications (ACE inhibitors, ARBs, beta blockers, calcium channel blockers, central alpha agonists, vasodilators [specifically, hydralazine and minoxidil])
device deficiency assessment	At each clinical encounter, participants will be asked about any unexpected signs or symptoms, as well as any device complaints/difficulties or alarms
treatment with Quanta SC+ DDS	During in-clinic phase, 3 sessions per week, 4 hours each session or as per clinic standard for training. During in-home phase, 4 sessions per week, 3.5 hours each session. During both phases, heparinization before and during each session if prescribed
Usability	Participants queried: required assistance with any aspect of treatment over the prior 7 days and if so, with which of the following tasks: machine set up, clearing of alarms, machine take down, fistula/needling or catheter connection
time to recovery	TTR is completed once after a dialysis treatment during the week of C1 – H1 – H4 and H8 or at withdrawal; not all treatments within those weeks. ( Lindsay 2006 )
treatment parameters	Review of dialysis prescription
treatment adequacy	Mid-week during each study period, determination of Kt/V
EQ-5D-5L	Quality of life assessment, patient reported
MOS sleep index	Quality of sleep assessment, patient reported
RTSQ	Renal treatment satisfaction, patient reported
ZBI12	Caregiver burden, caregiver reported ( ZBI12, Bédard 2001 )
ESAS-r	patient experience, patient reported ( Davidson SN., 2006 )
clinical utility	Number of alarms, time to resolve alarms, type of alarms. A report will be provided by Quanta at the end of treatment, either H8 or Withdrawal for the site to upload into the eCRF.
reliability	Ability to deliver prescribed treatments
proportion of participants and caregivers successfully trained	Measured by passing training competency by the end of clinic visits (no longer than 8 weeks of clinic visits)
RO water/dialysate quality	During installation prior to initiation of therapy for all participants water will be tested for culture and endotoxins and then minimum of each month
vital signs	Prior to dialysis treatment: pulse, blood pressure, temperature (oral, tympanic, temporal), and weight both before and after dialysis treatment. During dialysis treatment: pulse and blood pressure every 30 minutes
in home visit	Mid weekly visits will occur after the transitional week. Blood draw for Kt/V (bloodwork done pre and post dialysis) Also biweekly/monthly safety bloodwork and water quality testing as per study schedule. Review data entry on the treatment flowsheet and assess adherence, reinforce as required. Assessment of device-related events or adverse events. Assessment of vascular access site for any signs of infection etc. and review with participant any issues with self cannulation. Vital signs assessed by participants, dispense consumables according to supply needs. These visits will be done in person or virtually as per the standard of care at the

	research centre.
review of HCP support and interactions	HCP support and interactions are intended to be available to participants as required by the study, but not to provide additional training, support, or oversight of the dialysis procedure. Any contact outside study-driven procedures will be documented for purpose of understanding need for additional health care support.

### 8.3.1 Blood collection

Each participant will be required to provide approximately 120 ml or 8 tablespoons of total blood for the duration of the trial. Samples will be collected as per standard of care and analyzed in the local laboratory. Samples will be collected for chemistry, hematology, and iron as per schedule of assessments.

For post dialysis, a blood sample will be collected at the conclusion of therapy by reducing the blood pump speed to 100 ml per minute. After one minute has elapsed at that blood flow rate, then the sample will be collected according to the standard of care.

During training and during the transition week, the participant will be instructed on how to draw their own blood samples. During visits H1–H8, the participants may be instructed on how to draw their own blood sample or bloodwork can be drawn by trained research staff.

### 8.3.2 Heparinization

If an initial heparin bolus is prescribed for treatment, then a heparin dose will be manually delivered to the participant with a syringe through a fistula needle 5 minutes before commencement of treatment. Heparin therapy during dialysis treatment will be prescribed according to institutional practices and at the discretion of the Investigator and delivered via the dialysis bloodlines. For participants with arterial venous fistula or graft access should not receive heparin within 30 minutes of the end of treatment.

### 8.3.3 RO Dialysis Water and Dialysate Microbiological Quality Testing

During device installation in center and in home and monthly thereafter, water and dialysate samples will be collected and tested for total viable count (TVC) and endotoxin levels.

For dialysis water results above the action limits of 50 CFU/ml or 0.125 EU/ml the device manufacturer instructions should be followed for conducting a thermal or chemical disinfection cycle, a new sample will be drawn and new test results obtained. In addition, the Sponsor will review the culture and disinfection logs and determine if the system should be removed from use. If still above the action limit upon retesting, the device will be removed from use. Results above the maximum allowable level of <100 CFU/ml or <0.25 EU/ml may be considered a failure and the device removed from use.

For dialysate results above the action limits of 50 CFU/ml or 0.25 EU/ml a hot rinse thermal disinfection should be carried out, a new sample will be drawn and new test results obtained. In addition, the Sponsor will review the culture and disinfection logs and determine if the system should be removed from use. If still above the action limit upon retesting, the device will be removed from use. Results above the maximum allowable level of <100 CFU/ml or <0.5 EU/ml may be considered a failure and the device removed from use.

### 8.3.4 Treatment Flowsheet

During the course of the study, participants will utilize the treatment flowsheet to document medical device data and participant data in the home setting. Participants will be trained on how to document on the flowsheet during the clinic phase. Participants will begin documenting on the flowsheet during the transition phase and home phase. The information recorded on the flowsheet is as defined in the Informed Consent and Personal Health Information Use and Disclosure Authorization Form. The participants will be responsible for documenting on the flowsheet each time the patient receives treatment on the SC+.

### 8.3.5 Dialysis Supplies

The following supplies will be provided by Quanta:

- Cartridge (blood tubing set)
- Dialysis Cartridge
- Tablet for accessing applications for connected devices
- Bluetooth connected blood pressure monitor and scale

Note: All supplies will be returned to Quanta at the end of the study.

The following supplies will be provided by the investigator/ the treating center:

- Dialyzer (within specification as per user manual)
- saline
- dialysis needles
- cleaner for vascular access site
- gauze pads and tape for vascular access
- gloves, mask and safety glasses
- biohazard box and bag
- container of acid concentrate
- container of bicarbonate concentrate
- 20 cc syringe
- Heparin (per Subject's prescription) and syringe for administration
- recirculator
- cleaning supplies for machine after each treatment
- on-off kit for central venous catheter when applicable

### 8.3.6 Dialysis Prescription

The prescription for dialysis will include

- filter type used
- time on dialysis (180–240 min)
- blood flow rate (250–400 ml/min)
- dialysate flow rate (500 ml/min)
- dialysate Temp (35–37°C)
- Dialysate Conductivity (13.7 – 14.1 mS/cm)
- heparin dose and parameters
- ultrafiltration parameters and target weight
- acid concentrate composition
- Bicarbonate (35 mmol/L)

- blood pressure parameters for ultrafiltration

As much as possible unless medically necessary, the dialysis prescription should be kept constant during the study except for the change from 3 times per week, 4 hours per treatment during the in-clinic portion and 4 times per week, 3.5 hours per treatment during the transition and home portions. The prescription should not be changed for efficacy or other reasons unless medically indicated.

## **8.4 Participant Responsibilities Before, During, and After Treatment**

### **8.4.1 Participant Responsibilities Before Treatment**

Prior to treatment, participants will be responsible for:

- setting up device as per instructions,
- checking water for chlorine or chloramine (as per local protocol)
- measuring weight, blood pressure, pulse, and temperature and entering measurements on to the flowsheet,
- examining vascular access either by examining their fistula for signs of infection, thrill, bruit, aneurysms, and integrity of skin over the fistula or their central venous catheter site for any signs or symptoms of infection, and
- preparing dialysis access (catheter, fistula, or graft) using trained aseptic technique, and perform cannulation of the fistula or graft, or connection to a catheter.

### **8.4.2 Participant Responsibilities During Treatment**

During treatment, participants will be responsible for:

- initiating dialysis and monitoring treatment according to center protocol,
- entering the treatment start time on the treatment flowsheet,
- performing blood pressure and pulse readings every 30 minutes and entering measurements on the treatment flowsheet,
- answering questions on the patient flowsheet,
- refraining from eating and drinking as much as possible, and if not possible, recording amounts of fluid and food intake under the “Medical issues – Other” section on the treatment flowsheet,
- documenting on the treatment flowsheet any details of symptoms experienced during dialysis.
- performing their own blood draws during visits H1–H8 as appropriate.

### **8.4.3 Participant Responsibilities After Treatment**

After treatment, participants will be responsible for:

- measuring participant weight, blood pressure, pulse, and temperature and entering measurements on the treatment flowsheet, and documenting time to recovery disconnecting from dialysis treatment as instructed,
- answering question regarding general well being and treatment end time on the treatment flowsheet.
- cleaning device as instructed.

## 9 SAFETY

### 9.1 Adverse Event Definitions

Events will be classified based on the following definitions:

#### 9.1.1 Adverse Event

Any Adverse Event is defined as any untoward medical occurrence, unintended disease or injury, or untoward clinical signs (including abnormal laboratory findings) in participants, users or other persons, whether or not related to the investigational medical device.

#### 9.1.2 Device Related Adverse Event

Any adverse event related to the use of the medical devices listed for use in the study.

#### 9.1.3 Serious Adverse Event/Serious Adverse Device Effect

Any Adverse Event or Device Related Adverse Event with any one or more of the following characteristics:

- Led to or could have led to death
- Led to or could have led to serious deterioration in the health of the participant, resulting in
  - a life-threatening illness or injury
  - a permanent impairment of a body structure or a body function
  - in-patient or prolonged hospitalization
  - medical or surgical intervention to prevent life-threatening illness or injury or permanent impairment to a body structure or a body function
- Led to or could have led to fetal distress, fetal death, or a congenital abnormality or birth defect.

#### 9.1.4 Unanticipated Serious Adverse Device Effect

An unanticipated adverse device effect (UADE) is any serious adverse effect on health or safety, any life-threatening problem or death caused by, or associated with a device, if that effect, problem, or death was not previously identified in nature, severity, or degree of incidence in the application; or any other unanticipated serious problem associated with a device that relates to the rights, safety, or welfare of participants.

### 9.2 Adverse Event Relationship

All adverse events will be assigned an initial attribution according to the Investigator's believed primary cause. Events will be categorized by relationship to the investigational device, index procedure, concomitant medications, pre-existing condition, intercurrent condition, intercurrent intervention, or other.

*Investigational Device Related Adverse Event:* An adverse event, which in the judgment of the Investigator, results from use of the Quanta SC+ DDS.

*Non-Investigational Device:* It is reasonable to believe that the event is associated with an accessory device used during the study procedure and is not specific to the investigational device use

*Procedure Related Adverse Event:* An adverse event which, in the judgment of the Investigator, results as a consequence of dialysis independent of the use of the Quanta SC+ DDS.

*Medication-Related Adverse Event:* an adverse event is considered to be medication related when, in the judgment of the Investigator, it is reasonable to believe that the event is associated with any medications used.

*Pre-Existing Condition-Related Adverse Event:* an adverse event is considered to be related to a pre-existing condition when, in the judgment of the Investigator, it is reasonable to believe that the event is associated with the participant's pre-existing condition and is not specific to the investigational device or index procedure or medication to address heart failure. Pre-existing conditions that are aggravated or become more severe during or after the index procedure should be evaluated on a case-by-case basis to determine if the event may be more appropriately classified as device- or index procedure-related.

*Intercurrent Condition:* It is reasonable to believe that the event is directly associated with an intercurrent condition/co-morbidity.

*Intercurrent Intervention:* It is reasonable to believe that the event is directly associated with an intercurrent intervention which was performed for reasons other than to address a device- or index procedure-related complication.

*Observation/Incidental Finding:* Abnormal or non-specific findings or observations that may be associated with study activities but no identifiable clinical correlation and suggests no specific pathophysiological process (such as painful access or tired). Such an event will not be considered an adverse event unless associated with clinical sequelae or requires specific intervention. When clinical sequelae occur or when the intervention required exceeds standard response for similar symptom or event, it will be reported as an adverse event.

*Unknown:* The adverse reaction cannot be judged because information is insufficient or contradictory, and cannot be supplemented or verified.

### **9.3 Adverse Event Severity**

The severity of adverse events will be rated according to the following scale:

*Mild:* asymptomatic or mild symptoms; clinical or diagnostic observations only; intervention not indicated; event does not generally interfere with usual activities of daily living.

*Moderate:* minimal, local, or noninvasive intervention may be indicated; event interferes with usual activities of daily living, causing discomfort but poses no significant or permanent risk of harm to the research participant.

*Severe:* medically significant but not necessarily immediately life-threatening; hospitalization or prolongation of hospitalization indicated and may require intensive therapeutic intervention to resolve.

### **9.4 Adverse Events Recording and Reporting**

#### **9.4.1 All Adverse Events**

All Adverse Events and Device Related Adverse Events will be recorded as part of this study beginning from first treatment with the Quanta SC+ DDS. Participants will be asked at each encounter an open-ended question such as, "How have you been feeling since your last visit?" and any events meeting an adverse event definition will be recorded. Clinic progress notes and other medical records will also be reviewed to determine if adverse events have occurred.

All adverse events (i.e., serious or non-serious, anticipated or unanticipated) must be recorded on the Adverse Event CRF by the Investigator or designee, for events of hypotension a specific eCRF should be used to ensure all details regarding event are recorded. All device deficiencies should be recorded on the device observations eCRF. The record must include the start date of the adverse event, treatment, resolution, and assessment of both the seriousness and the relationship to the investigational device.

The following criteria must also be adhered to by the Investigator:

- Completion of a separate Adverse Event form or log entries to document each event
- Completion of separate device observation form or log entries for each device observation or deficiency
- Electronic signature of forms or log entries
- On request of the sponsor, provision of any additional information related to the safety reporting of a particular event

All adverse events will be reported by the Sponsor or designee to the applicable regulatory authority at least annually or as required and to IRBs as instructed by the applicable IRB.

#### **9.4.2 Serious Adverse Events**

All serious adverse events (including SADE and USADE) should be reported by the Investigator (or designee) by submitting the Adverse Event Electronic Case Report Form to the Sponsor within 24 hours of learning of the adverse event.

The Investigator (or designee) shall provide source documents related to the serious and/or unanticipated adverse event as requested by Sponsor or their designee.

The Investigator must follow all unresolved serious adverse events until the events are resolved, the participant is lost to follow-up, the participant has withdrawn consent, or the adverse event is otherwise explained.

The Sponsor will evaluate all serious adverse events for reportability as an unanticipated adverse device effect in accordance with 21CFR812.46(b). The investigator and Sponsor will comply with reporting requirements per 21CFR812.150. A sponsor who conducts an evaluation of an unanticipated adverse device effect under 21CFR812.46(b) shall report the results of such evaluation to FDA and to all reviewing IRBs and participating investigators within 10 working days after the Sponsor first receives notice of the effect. Thereafter the Sponsor shall submit such additional reports concerning the effect as FDA requests.

Study sponsor, or their designee, in cooperation with the Investigator, will assess all serious adverse events considered device-related for potential reportability to the FDA as an Unanticipated Serious Adverse Device Effect (USADE). Any unanticipated adverse events: must also be reported to the FDA, all reviewing IRBs, and participating investigators within ten (10) days of receiving notice of the serious adverse event or death, (or per local IRB requirements), and documentation of the report sent to Sponsor or their designee.

It is the responsibility of the Investigator to inform their IRB of serious adverse events as required by their IRB procedures and in conformance with applicable regulatory requirements.

In the event of a suspected device observation or deficiency, the device shall be returned to Sponsor for analysis. Instructions for returning the investigational device are included in the Study Reference Manual. The device will be replaced as appropriate.

#### 9.4.3 Pregnancy

Pregnancy itself is not an adverse event. Participants of childbearing potential will be instructed that they must use medically acceptable birth control during the trial. Should a participant become pregnant, they will be followed to live birth or other outcome and any adverse events related to childbirth or fetal or newborn abnormalities will be recorded and followed to resolution or 30 days post birth.

#### 9.4.4 Death of Participants

Participant death during the investigation should be reported with written documentation to Sponsor or designee within 24 hours of Investigator's knowledge of the death. The adverse event that resulted in death should be entered in the database within 24 hours and include a brief description of the relevant details of the death. The electronic Adverse Event Form must be electronically signed by the Investigator. A copy of the death records, death certificate and an autopsy report (if performed) are required to be sent to the Sponsor or designee within 10 days following the death. In addition, participant death must be reported to the IRB in accordance with IRB requirements.

### 10 STATISTICAL CONSIDERATIONS

#### 10.1 Statistical Overview

Baseline characteristics will be summarized for all participants using conventional summary statistics reported as mean and standard deviation or median and interquartile range, as appropriate.

#### 10.2 Sample Size for Primary Endpoint

##### 10.2.1 Primary Effectiveness Endpoint

The primary effectiveness endpoint is the delivery of a weekly standard Kt/V of greater than or equal to 2.1. The hypotheses are outlined in Section 10.4.1 below, and the analysis will be done in each of the In-Center period and the In-Home period. The sample size was derived based on the following assumptions:

- True treatment period mean weekly standard Kt/V is 2.5
- Standard deviation is 0.7
- One-sided  $\alpha=0.025$
- Within patient correlation of  $\rho=0.50$
- AR(1) covariance structure

Using a one-sample test, a sample size of  $n=11$  patients, each measured weekly for 8 weeks of treatment, will have >90% power to detect that the mean weekly standard Kt/V is greater than 2.1.

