### Treatment number versus Kt/V

The mean urea reduction ratio (URR) for available blood data was 74.4% with a standard deviation of 7.1%.

All reported adverse event observations related to complications commonly noted during hemodialysis treatment such as hypotensive episodes. No deaths or hospitalizations were reported. Measured NFR figures showed an apparent bias due to a measurement error. One adverse device effect was reported, however the Quanta SC+ DDS safety mechanism functioned correctly and protected the patient from harm.

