4 SAMPLE SIZE

Sample size for analysis of primary effectiveness endpoint was calculated using a one-sample test. It was determined that a sample of n=11 patients, each measures weekly for 8 weeks of treatment, will have >90% power to detect that the mean weekly standard Kt/V is greater than 2.1. Sample size was calculated under the following assumptions:

- True treatment period mean weekly standard Kt/V is 2.5
- Standard deviation is 0.7
- One-sided $\alpha=0.025$
- Within patient correlation of $\rho=0.50$
- AR(1) covariance structure

Sample size for primary safety endpoint was calculated using a two-sample t-test. It was determined that a sample size of n=33 patients, with 4 dialysis intervals per week for 8 weeks, would have >90% power to demonstrate the rate of AEs per 100 treatments is no more than 10% higher in the in-home period compared to the in-center period. Sample size was calculated under the following assumptions:

- $\mu_{IH} = 0.03$, the rate of AEs per dialysis treatment in-Home is 0.03
- $\mu_{IC} = 0.03$, the rate of AEs per dialysis treatment in-Center is 0.03
- $\mu_{IH} - \mu_{IC} = 0$, the difference in rate of AEs per dialysis treatment is 0
- $\sigma_{IH-IC} \leq 0.17$, the standard deviation of the difference is less than 0.17 AEs per dialysis interval
- Non-inferiority margin of 0.1 AEs per dialysis interval
- One-sided $\alpha=0.025$

To account for an expected 15% lost to follow-up rate, and an additional 2 expected death or transplant events during the 8 week in-home phase, based on a combined rate of death and transplant of approximately 15 per 100 patient-years in a usual home hemodialysis (HHD) population, up to 50 patients will be enrolled to yield the 33 evaluable patients needed to be sufficiently powered for both the primary efficacy and primary safety endpoints.

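### The >90% power stated for 11 patients with 8 weekly Kt/V values does not hold for the in-center test, which may have only 4 values per patient (66–75%); the planned 33 evaluable patients remain enough

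*Protocol*

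**What the plan says.** Protocol 10.2.1 states that the effectiveness analysis is done separately in the In-Center and In-Home periods. It then gives one calculation for both. The assumptions are "True treatment period mean weekly standard Kt/V is 2.5", "Standard deviation is 0.7", one-sided alpha 0.025, within-patient correlation 0.50 and an AR(1) structure. The conclusion is that 11 patients, "each measured weekly for 8 weeks of treatment, will have >90% power to detect that the mean weekly standard Kt/V is greater than 2.1". The method is described only as a one-sample test. SAP 4 repeats the inputs and the result: "each measures weekly for 8 weeks of treatment, will have >90% power".

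The two periods differ in length. The home period is 8 weeks. For the clinic period, Protocol 8.2 says "In-clinic dialysis will continue for a minimum of 4 weeks". It is extended week by week, normally to at most 8 weeks, and only while training competence has not been shown (Protocol 6.5, 7.3 and footnote 1 to the Schedule of Assessments). Kt/V is measured once a week (footnote 5).

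Protocol 10.4 and SAP 7.5 require both effectiveness hypotheses to succeed. Protocol 10.2.2 and SAP 4 set the trial at 33 evaluable patients out of 50 enrolled (up to 50 in the SAP), and describe 33 as sufficient for both primary endpoints.

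**The concern.** The calculation counts 8 values per patient for a test that is guaranteed only 4. Fewer weekly values make each patient's period mean less precise, so 11 patients do not give the stated power in-center. That test is not optional: if it fails, the trial fails its success criterion.

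The documents give no effectiveness power at 33 patients. The statement about 11 is therefore the only numerical support for calling the trial adequately powered for effectiveness, and it does not describe one of the two tests.

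**Working it through.** **Inputs** (Protocol 10.2.1, SAP 4): difference 2.5 − 2.1 = 0.4; SD 0.7; AR(1) correlation 0.5; one-sided alpha 0.025, so z = 1.960; n = 11. Values per patient: m = 8 at home, m = 4 as the in-center minimum with no weekly value missing.

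**Formulas**

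- Variance factor for the mean of m AR(1) values: f(m) = [m + 2 Σ (m − k) 0.5^k] / m², with k from 1 to m − 1.
- Standard error: SE = 0.7 × √(f/n).
- Normal power: Φ(0.4/SE − 1.960).
- t power: noncentral t on the patient means, n − 1 degrees of freedom, noncentrality 0.4/SE.

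**Reproducing the plan's figure (m = 8)**

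- f(8) = (8 + 2 × 6.0078)/64 = 0.3127.
- SE = 0.7 × √(0.3127/11) = 0.1180.
- Normal power = Φ(3.389 − 1.960) = Φ(1.429) = 92%.
- n = 10 gives 89.8%, so 11 is the smallest n that reaches 90%. This is very probably how the figure arose.
- By t with 10 degrees of freedom the power is 86%, and 90% needs n = 13. With the larger degrees of freedom a repeated-measures model might use (77 to 87), it is about 92%.

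**The in-center minimum (m = 4)**

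- f(4) = (4 + 2 × 2.125)/16 = 0.5156.
- SE = 0.7 × √(0.5156/11) = 0.1516.
- Normal power = Φ(2.639 − 1.960) = Φ(0.679) = 75%.
- By t with 10 degrees of freedom the power is 66%; a simulation of 100,000 trials also gave 66.3%. With 33 to 43 degrees of freedom it is about 73%.
- For 90%, normal: n ≥ (1.960 + 1.282)² × 0.49 × 0.5156/0.16 = 16.6, so 17. By t, 19.

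**Between the minimum and the maximum, n = 11**

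| In-center values per patient | Normal | t, 10 df |
|---|---|---|
| 4 | 75% | 66% |
| 5 | 81% | 73% |
| 6 | 86% | 78% |
| 7 | 90% (89.5%) | 83% |
| 8 | 92% | 86% |

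Like for like, going from 8 values to 4 lowers power from 92% to 75% (normal) or from 86% to 66% (t).

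**At the planned 33 evaluable patients**

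- In-center, m = 4: SE = 0.7 × √(0.5156/33) = 0.0875. Normal power = Φ(4.571 − 1.960) = 99.5%; t 99.3%.
- Home, m = 8: above 99.9% by either method.
- Jointly, as a product assuming independence: 99.5% (normal) or 99.3% (t).
- Sensitivity with constant correlation 0.5, m = 4: f = (1 + 3 × 0.5)/4 = 0.625, giving 98.6% (normal) or 98.1% (t).

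**The case against.** The best defense has three parts, and each stands.

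- **Eleven is not the trial's sample size.** The plan provides three times as many evaluable patients, and at 33 the in-center test is well powered even with 4 values each.
- **The stated figure is not an arithmetic slip.** It reproduces for the 8-week home period under a normal approximation. The documents name neither a t-test nor 10 degrees of freedom, and the planned analysis is a repeated-measures ANOVA with AR(1). The 66% should therefore not be set against the stated >90% as if only the weeks had changed; that comparison changes the test as well.
- **Four values is the minimum.** Patients who need C5 to C8 contribute more.

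What remains is that Protocol 10.2.1 applies the 8-value calculation to a period that need not supply 8 values. None of the methods tried reaches 90% with 11 patients and 4 values.

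Two stronger readings are tempting but not supported:

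- **Constant correlation as the true structure.** This would lower every figure, but AR(1) is the stated assumption and matches the analysis model. Constant correlation is a sensitivity case.
- **A low in-center mean.** Protocol 5.6.2 reports, for the pilot study, "The mean urea reduction ratio (URR) for available blood data was 74.4% with a standard deviation of 7.1" percent. A reader might convert this to a mean standard Kt/V well under 2.5 for the clinic prescription and conclude that even 33 patients are too few. The pilot section gives no session length, weekly frequency or ultrafiltration volume for those samples; the 4-hour target in 5.6.1 belongs to a different study. Such a reading would also join a pilot-based mean to the planning SD of 0.7, which is not shown to come from the pilot. It gives no usable power figure.

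**Conclusion.** The stated power holds for the in-home test under a normal approximation and fails for the in-center test. At 11 patients and the in-center minimum of 4 values, power is 66% to 75% depending on the test, and the number needed for 90% is 17 to 19. These figures take the plan's mean, SD, correlation and alpha as given and assume no missing weekly values.

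A reader might infer that the trial is underpowered for effectiveness. On the plan's own assumptions it is not: 33 evaluable patients give about 99% power in-center and about 99% jointly. That reassurance depends on the planning mean of 2.5 and SD of 0.7; this check does not test whether those values are right. The defect is a wrong statement about a required test, not a wrong trial size.

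**What to change.** In Protocol 10.2.1 and SAP 4, replace the single statement about 11 patients with figures for each period:

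- In-center: 4 to 8 weekly values per patient, with power at the minimum of 4.
- In-home: 8 weekly values per patient.
- The test and degrees of freedom behind each figure.
- Power at 33 evaluable patients for each test and for both together, with the assumption used to combine them. Under the stated inputs these are about 99% in-center at 4 values, above 99.9% at home, and about 99% jointly.
- As a sensitivity figure, about 98% in-center by t if the correlation is constant at 0.5.

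Both documents should change together, because the SAP repeats the protocol's statement. The cost is a text edit; no data collection, analysis method or enrollment target changes.
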